# EFFECTIVENESS OF ULTRASONOGRAPHY IN THE EVALUATION OF DIFFICULT AIRWAY IN OBESE PATIENTS

## INTRODUCTION

Obesity has become an increasing public health problem worldwide. Obesity-related changes in pulmonary mechanics and metabolic, cardiovascular and respiratory physiology increases the risk of mortality and morbidity in the perioperative period.

Obesity is a proinflammatory multisystemic disease defined as hypertrophy and/or hyperplasia of adipose tissue. Genetic characteristics, endocrine disorders, neurological, psychological and environmental factors are effective in the development of obesity. Obesity is classified according to body mass index. Body Mass Index (BMI) is defined as the ratio of body weight in kilograms (kg) to the square of height in meters (m). According to the World Health Organization (WHO), obesity is a global epidemiological epidemic and there are 1.5 billion obese patients worldwide.

Obesity is a main factor causing difficulties in airway management. Difficult airway is characterized by difficult mask ventilation and difficult intubation. It is more frequent in obese patients, because the neck is short and thick, and the larynx is displaced anteriorly and upwards. The amount of pharyngeal and palatal soft tissue is increased and the tongue is enlarged. Difficulty should be expected in providing airway management such as mask ventilation, direct laryngoscopy and tracheostomy, as a result of the enlargement of the face, neck, chest and abdomen circumferences with a high Mallampati score. The incidence of difficult intubation in patients with BMI > 35 kg/m^2 has been reported as 15.5%. But the literature also states that difficulty in intubation is not related to BMI but due to large neck diameter and mallampati score III-IV. The probability of difficult intubation was 5% in those with a neck circumference of 40 cm and 35% in those with a neck circumference of 60 cm^5. Indicators of difficult intubation in the pre-operative assessment are small oral cavity, short neck, limited head and neck movements due to increased fat tissue, mallampati score 3 or higher, sternomental distance of 12.5 cm or thyromental distance of less than 6 cm^6.

Ultrasonography is a low-cost, safe and rapid evaluation method. Some studies show that the measurement of soft tissue thickness in the anterior neck at the level of the vocal cords plays an important role in predicting difficult laryngoscopy in obese patients. Airway evaluation with ultrasonography can be performed in emergency departments, intensive care units and operating rooms. In addition to the upper airway evaluation, the lower airway, lungs and pleura can also be evaluated. Again, difficult intubation is envisaged in patients with pretracheal soft tissue thickness of 28 mm and neck circumference of more than 50 cm at the level of the vocal cord.

In this study, it is aimed to determine the correlation between ultrasonographic measurements (anterior cervical soft tissue thickness at the level of the skin-anterior vocal cord junction, the distances between skin-hyoid bone, skin-thyrohyoid membrane, skin-midpoint of

the epiglottis) and difficult mask ventilation (Han Scale) and difficult laryngoscopy (Cormack-Lehane Classification) in obese patients ( $BMI \geq 30 \text{ kg/m}^2$ ).

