## METHODS AND MATERIALS

A total of 150 patients ages between 18-80 years,  $BMI \geq 30 \text{ kg/m}^2$ , ASA I-III who will undergo elective surgery under general anesthesia will be included in the study. Patients with facial and cervical trauma or cancer surgery, tracheostomy or thyroid surgery, non-cooperative patients and pregnant women will be excluded.

During the pre-operative evaluation gender, age, height, weight, type of surgery, BMI, neck circumference and extension, thyromental distance, sternomental distance, hyomental distance, mouth opening and distance between incisors will be measured to evaluate the dentition. ASA physical status will be recorded. OSAS will be evaluated based on Apnea-Hypopnea Index (AHI) ( $AHI < 5$  simple snoring,  $5 \leq AHI < 15$  Mild OSAS,  $15 \leq AHI < 30$  Moderate OSAS,  $AHI \geq 30$  Severe OSAS). Modified Mallampati Score will be recorded. During this test, the pharyngeal structures will be evaluated by having the patient open his/her mouth as much as possible and protrude his/her tongue forward as much as possible in the neutral position without making a sound. (Class I: uvula, soft palate, tonsil bed, anterior and posterior plicae can be easily seen. Class II: uvula and soft palate can be seen. Class III: soft palate and base of the uvula are visible. Class IV: the uvula is completely covered by the tongue root and the pharyngeal wall cannot be seen). Patients will have an upper lip bite test. In order to perform the upper lip bite test, the patients will be asked to bite their upper lip with their lower incisors. According to this test; if the patient can bite the upper lip above the vermilion with the lower incisors, he/she will be evaluated as class 1; if the patient can bite the upper lip below the vermilion with the lower incisors, he/she will be evaluated as class 2; if the patient cannot bite the upper lip with the lower incisors, he/she will be evaluated as class 3. In accordance with the original study, class 1 and 2 will be considered as easy and class 3 as difficult intubation criteria.

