Ultrasonographic measurements will be performed by the main researcher anesthesiologist with the patient in supine position with head and neck placed neutrally. Anterior cervical soft tissue measurement will be performed in the transverse plane with a 13-6 MHz linear USG probe (Sonosite M-Turbo), including the hyoid bone, thyrohyoid membrane and anterior vocal cord junction. At the level of the hyoid bone, the minimum distance between the hyoid bone and skin (HCM) will be measured and recorded; at the level of the thyrohyoid membrane, the distance between the epiglottis midpoint and skin (ECM) between the hyoid bone and thyroid cartilage; and at the level of the vocal cord, the distance between the vocal cord anterior junction and skin (VCM) will be measured and recorded.

Train of four (TOF) monitoring will be applied to all patients along with standard anesthesia monitoring. Standard induction of anesthesia, 2 mg/kg propofol, 2 mcg/kg fentanyl, 0.6 mg/kg rocuronium as standard to be done intravenously. Mask ventilation will be done with a disposable plastic mask. The Han Scale will be used to assess difficult mask ventilation. (Class 1- Easy mask ventilation, Class 2- Oral airway / adjuvant requirement with/without NMBA,

Class 3- Inadequate, difficult and unstable two practitioners with/without NMBA, Class 4- Impossible with/without NMBA ventilation) The laryngoscopy procedure will be performed by an anesthesiologist who has a minimum of 2 years of anesthesia experience and does not know about USG measurements, with an appropriate size Macintosh blade, after adequate muscle relaxation. The laryngoscopy image will be evaluated with the Cormack-Lehane classification. (Class 1- Glottis fully visible, Class 2- a. Glottis partially visible b. Only arytenoid cartilages visible, Class 3- Only epiglottis visible, Class 4- Epiglottis or glottis not visible) Han Scale 3-4 difficult mask ventilation, Cormack-Lehane 2b-4 will be considered difficult laryngoscopy.

[figure not shown]

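### Does recording no intubation outcome leave half of the protocol's target condition unmeasured?

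*Protocol*

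**What the plan says.** The title, "EFFECTIVENESS OF ULTRASONOGRAPHY IN THE EVALUATION OF DIFFICULT AIRWAY IN OBESE PATIENTS", names the difficult airway as the condition to be evaluated. The Introduction describes that condition in one sentence: "Difficult airway is characterized by difficult mask ventilation and difficult intubation". Several background figures there concern intubation. Its incidence above a BMI of 35 kg/m² "has been reported as 15.5"%, its probability is put at 5% and 35% for neck circumferences of 40 cm and 60 cm, and a pretracheal thickness of 28 mm is linked to it.

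The Introduction closes with the aim, which is narrower. The ultrasound distances are to be correlated with "difficult mask ventilation (Han Scale) and difficult laryngoscopy (Cormack-Lehane Classification) in obese patients".

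Methods and Materials follows the aim. For the first outcome, "The Han Scale will be used to assess difficult mask ventilation". For the second, "The laryngoscopy image will be evaluated with the Cormack-Lehane classification". The cut-offs are then fixed: "Han Scale 3-4 difficult mask ventilation, Cormack-Lehane 2b-4 will be considered difficult laryngoscopy". In that section the term difficult intubation serves only to label the upper lip bite test, where "class 1 and 2 will be considered as easy and class 3 as difficult intubation criteria". The text names no number of attempts, time to intubation, failed intubation, change of device or operator, or intubation difficulty score.

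**The concern.** The title promises an evaluation of the difficult airway, and the only sentence that says what this means has two parts. One part, mask ventilation, has its own scale. The other, intubation, has no recorded outcome. A poor laryngoscopic view and a difficult intubation are different events: the first describes what is seen, the second whether and how readily the tube is placed.

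If the target condition really were the pair named in that sentence, the study could not say whether ultrasound identifies difficult intubation. Its rates could not be set beside the intubation rates that it cites, and the bite-test label would have no matching event to be checked against. The omission would also lie beyond the reach of a statistical analysis plan, because a variable that is never collected cannot be analysed.

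**Working it through.** No arithmetic beyond a count applies. The protocol's only design figure is the sample size of 150, and the question does not depend on it. The check is to set each part of the document against what is measured.

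| Place in the protocol | Construct named | Role in the document | Measured? |
|---|---|---|---|
| Title | Difficult airway | Topic | Through the two outcomes below |
| Introduction, description of difficult airway | Mask ventilation, intubation | Background | First directly; second only through the laryngoscopic view |
| Introduction, aim | Mask ventilation, laryngoscopy | Objective | Both |
| Methods and Materials, outcomes | Han 3-4, Cormack-Lehane 2b-4 | Outcomes with cut-offs | Both |
| Methods and Materials, upper lip bite test | Label of difficult intubation for class 3 | Pre-operative predictor | Predictor recorded; no outcome attached |

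**Which statement governs.** The outcomes that a study must deliver are those in its aim. The aim names two, each with its scale, and Methods and Materials measures two: 2 of 2. No stated objective lacks its outcome. A share of one half (1 of 2) arises only if the background sentence is taken as the list of outcomes and the Cormack-Lehane grade is given no credit for intubation.

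**Whether laryngoscopy appears from nowhere.** It does not. The Introduction cites work in which neck soft tissue thickness at vocal cord level helps to predict difficult laryngoscopy in obese patients. It also lists direct laryngoscopy among the airway tasks in which difficulty is to be expected. Rationale, aim and Methods therefore share a line that runs through laryngoscopy, alongside the figures on intubation.

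**Whether the second component is wholly without data.** The Cormack-Lehane grade is taken at laryngoscopy, with the operator unaware of the ultrasound measurements. It is an indirect measure of that component. The protocol does not call it a surrogate, but the statement that no patient has any information on this component goes too far.

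**Whether a planned analysis fails.** Each supposed loss can be held against the aim:

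- *Comparison with the 15.5%.* This figure is background. It is not an input to the sample size, and no comparison with it is an objective.
- *Checking the bite-test label.* The bite test is one of many pre-operative assessments. The protocol takes its easy/difficult split from the study that introduced the test and does not set out to validate it.
- *Prediction of intubation by ultrasound.* The aim makes no such claim.

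None of the three is an analysis that the protocol plans.

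**The case for a change.** The best case for a change runs as follows. The title still claims the difficult airway, and the Introduction is the only place that says what this is. Intubation is not confined to the background, since the bite-test rule stands in the Methods. The document uses laryngoscopy and intubation as separate terms and never says that the Cormack-Lehane grade stands in for intubation, so a reader may be tempted to set the rate of grades 2b-4 against the cited 15.5%. Details of an intubation are observed once, and two further items would cost little.

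Part of this stands. The wording is uneven, the surrogate role of the grade is not stated, and the text names no intubation outcome. Findings from this study cannot directly support statements about difficult intubation.

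The rest does not carry. Choosing the laryngoscopic view over attempts or adjuncts is a design choice that the aim states openly and the Methods define with a cut-off. An intubation outcome would answer a further question; it would not repair the answer to the one asked. Loss of the data is also not established, because the protocol does not say what the routine anaesthesia record holds. Narrower wording, the other possible remedy, is what the aim and the cut-off sentence already use. The protocol contains no conclusions to restrict, which leaves only the title.

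**Conclusion.** No change to the plan follows. Followed as written, the study measures both outcomes of its stated aim in the patients it enrols and can relate the ultrasound distances to each. None of the two stated outcomes is missing, so the figure of one half does not describe a real gap.

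What is left is a difference in terms: the title and part of the Introduction speak of the difficult airway and of intubation, while the aim and Methods speak of laryngoscopy. It affects no measurement, cut-off or planned analysis. A careful analyst or author deals with it by reporting results as difficult mask ventilation and difficult laryngoscopy, which are the protocol's own outcome terms.

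This rests on three assumptions. The aim, not the background description, fixes what the study must measure. The figures that are not shown hold nothing that alters the list of outcomes; an intubation item there would only weaken the concern further. The results will be stated for the outcomes measured; a claim about intubation itself would go beyond the data, but that would be a fault of reporting and not of this plan.

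### The only stated aim is a correlation, which cannot say how many difficult airways ultrasound detects or how many easy ones it flags wrongly

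*Protocol*

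**What the plan says.** - **Title:** "EFFECTIVENESS OF ULTRASONOGRAPHY IN THE EVALUATION OF DIFFICULT AIRWAY IN OBESE PATIENTS".
- **Introduction, last paragraph (the only aim):** "it is aimed to determine the correlation between ultrasonographic measurements" and "difficult mask ventilation (Han Scale) and difficult laryngoscopy (Cormack-Lehane Classification) in obese patients".
- **Methods and Materials, outcome definitions:** "Han Scale 3-4 difficult mask ventilation, Cormack-Lehane 2b-4 will be considered difficult laryngoscopy". The ultrasound distances are continuous, and no study cut-off is given for them.
- **Methods and Materials, upper lip bite test:** this bedside test is also sorted into two classes: "class 1 and 2 will be considered as easy and class 3 as difficult intubation criteria".
- **Methods and Materials, sample size:** "A total of 150 patients", with no stated basis.

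The laryngoscopist is kept unaware of the ultrasound measurements. Sensitivity, specificity, predictive values, ROC curves and AUC are not mentioned anywhere in the protocol.

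**The concern.** The title, the binary outcome definitions and the masking of the laryngoscopist all suit a study of how well a measurement separates difficult from easy airways. The aim names a different quantity. A reader of the result will want to know what share of difficult airways a given distance would detect, and what share of easy ones it would flag wrongly. A correlation supplies neither.

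Two consequences follow. A modest but statistically significant coefficient could be reported as showing that ultrasound is effective when its discrimination is poor. And if difficult mask ventilation and difficult laryngoscopy occur at different frequencies, their coefficients cannot be compared as measures of how well ultrasound works for each.

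**Working it through.** The protocol states no target correlation, accuracy or precision, so there is no figure of its own to reproduce. The check asks what a correlation would and would not determine under each reading of the aim.

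**Inputs from the protocol.** There are 150 patients. The Introduction reports difficult intubation in 15.5% of patients with BMI above 35. By neck size, it states: "difficult intubation was 5% in those with a neck circumference of 40 cm and 35% in those with a neck circumference of 60 cm". These figures concern difficult intubation. They are not for Cormack-Lehane 2b-4 or Han 3-4 at BMI 30 or more, so 5%, 15.5% and 35% serve only as illustration.

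**Assumption.** Distances are normal with equal variance within each outcome group or grade.

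**Reading 1: correlation with the binary outcome**

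Take a distance with AUC 0.75.

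- Standardised difference: d = √2 × Φ⁻¹(0.75) = 0.954.
- Specificity at 80% sensitivity: Φ(0.954 − 0.842) = 0.54, whatever the outcome frequency.
- Point-biserial r = d√(pq) / √(1 + d²pq), with q = 1 − p.
- Spearman = √(3pq) × (2 × AUC − 1).

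| Frequency p | pq | Point-biserial r | Spearman | AUC |
|---|---|---|---|---|
| 5% | 0.0475 | 0.20 | 0.19 | 0.75 |
| 15.5% | 0.1310 | 0.33 | 0.31 | 0.75 |
| 35% | 0.2275 | 0.41 | 0.41 | 0.75 |

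The coefficient doubles while the accuracy stays the same. In the other direction, d = r / √((1 − r²)pq). A fixed r of 0.30 then gives d = 1.44, 0.87 and 0.66, hence AUC = Φ(d/√2) = 0.85, 0.73 and 0.68.

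Statistical significance does not settle the matter. With 150 patients, r = 0.20 gives t = 0.20 × √(148/0.96) = 2.48, p = 0.014. At 15.5% frequency it corresponds to d = 0.20 / √(0.96 × 0.1310) = 0.56. That is an AUC of about 0.65 and a sensitivity of Φ(0.56 − 0.84) = 39% at 80% specificity.

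**Reading 2: correlation with the full Cormack-Lehane grades**

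Assume shares of 50 / 34.5 / 8 / 6 / 1.5% for grades 1, 2a, 2b, 3 and 4, so that 8 + 6 + 1.5 = 15.5% are difficult. Let the mean distance follow each pattern below, in units of the within-grade SD. Each pattern is scaled so that the tie-corrected Spearman coefficient is 0.30.

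| How the distance changes with grade | Mean by grade | AUC for 2b-4 | Specificity at 80% sensitivity |
|---|---|---|---|
| Only between 1 and the rest | 0.672 × (0,1,1,1,1) | 0.61 | 34% |
| Evenly | 0.369 × (0,1,2,3,4) | 0.71 | 47% |
| Only between 2a and 2b | 1.456 × (0,0,1,1,1) | 0.85 | 73% |

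The coefficient pools separation among the easy grades (1 v 2a) with separation at the protocol's own boundary (2a v 2b). With grade 1 at 35% and 2a at 49.5%, the outer AUCs are 0.58 and 0.85. With grade 1 at 65% and 2a at 19.5%, they are 0.64 and 0.82. A simulation of 1,000,000 patients at the base shares agreed (AUC 0.607, 0.710, 0.848).

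**The case against.** The strongest reply is that this belongs in the SAP. AUC, sensitivity, cut-offs and their intervals are commonly left to it, and an SAP that is not shown may contain them. In a short protocol, correlation may mean no more than relation. The binary definitions and the masking already point towards discrimination, and nothing rules out a ROC analysis. The title does not literally say diagnostic accuracy. A rank correlation with ordinal grades is a legitimate description, and on the binary reading Spearman at the observed frequency is only a rescaling of AUC. The numbers rest on assumed AUCs, grade shares and distributions, and the outer ordinal scenarios are extremes. Since distances and grades are recorded for every patient, a ROC analysis remains possible later.

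Much of this stands. The protocol does not contradict itself, the figures illustrate a general property and do not forecast this study, and no data would be lost. What does not stand is moving the point wholly to the SAP. The aim is a protocol statement that names a quantity, and accuracy analyses in an SAP would go beyond the only aim the protocol declares. Reading correlation loosely as association leaves the same gap, because association also gives no detection or false-alarm rate. Rescaling Spearman to AUC still yields no sensitivity or specificity.

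**Conclusion.** The concern holds as a worthwhile and inexpensive improvement to the aim. Met exactly as written, the aim would not answer the question in the title. In the illustrations, one level of accuracy (AUC 0.75) produces correlations from 0.20 to 0.41 depending on frequency. One ordinal correlation (0.30) is compatible with AUCs from 0.61 to 0.85, and with specificities from 34% to 73% at 80% sensitivity.

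These sizes depend on equal-variance normal distances, on borrowed frequencies for difficult intubation, and on assumed grade shares. The conclusion that a correlation does not fix sensitivity or specificity needs none of those values.

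**What to change.** Restate the aim along these lines: to estimate the discrimination of each ultrasonographic distance for Cormack-Lehane 2b-4 and for Han 3-4. Report the AUC with its 95% CI, plus sensitivity and specificity with 95% CIs. State that any cut-off chosen from these data is exploratory. Keep correlations, including those with the full ordinal grades, as description.

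The cost is one reworded sentence and a standard ROC analysis of data already to be collected. No procedure or outcome definition changes.

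The downside is that imprecision becomes visible. With 150 patients, 15.5% gives about 23 difficult cases and 5% gives about 8 (150 × 0.155 = 23.25; 150 × 0.05 = 7.5).

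| Difficult / easy | Hanley-McNeil SE at AUC 0.75 | 95% half-width (1.96 × SE) | Example sensitivity | Exact 95% CI |
|---|---|---|---|---|
| 23 / 127 | 0.062 | 0.12 | 18/23 = 78% | 56% to 93% |
| 8 / 142 | 0.102 | 0.20 | 6/8 = 75% | 35% to 97% |

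That uncertainty exists whichever quantity is reported. Showing it guards against over-reading a significant correlation.

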## METHODS AND MATERIALS

A total of 150 patients ages between 18-80 years,  $BMI \geq 30 \text{ kg/m}^2$ , ASA I-III who will undergo elective surgery under general anesthesia will be included in the study. Patients with facial and cervical trauma or cancer surgery, tracheostomy or thyroid surgery, non-cooperative patients and pregnant women will be excluded.

During the pre-operative evaluation gender, age, height, weight, type of surgery, BMI, neck circumference and extension, thyromental distance, sternomental distance, hyomental distance, mouth opening and distance between incisors will be measured to evaluate the dentition. ASA physical status will be recorded. OSAS will be evaluated based on Apnea-Hypopnea Index (AHI) ( $AHI < 5$  simple snoring,  $5 \leq AHI < 15$  Mild OSAS,  $15 \leq AHI < 30$  Moderate OSAS,  $AHI \geq 30$  Severe OSAS). Modified Mallampati Score will be recorded. During this test, the pharyngeal structures will be evaluated by having the patient open his/her mouth as much as possible and protrude his/her tongue forward as much as possible in the neutral position without making a sound. (Class I: uvula, soft palate, tonsil bed, anterior and posterior plicae can be easily seen. Class II: uvula and soft palate can be seen. Class III: soft palate and base of the uvula are visible. Class IV: the uvula is completely covered by the tongue root and the pharyngeal wall cannot be seen). Patients will have an upper lip bite test. In order to perform the upper lip bite test, the patients will be asked to bite their upper lip with their lower incisors. According to this test; if the patient can bite the upper lip above the vermilion with the lower incisors, he/she will be evaluated as class 1; if the patient can bite the upper lip below the vermilion with the lower incisors, he/she will be evaluated as class 2; if the patient cannot bite the upper lip with the lower incisors, he/she will be evaluated as class 3. In accordance with the original study, class 1 and 2 will be considered as easy and class 3 as difficult intubation criteria.

Ultrasonographic measurements will be performed by the main researcher anesthesiologist with the patient in supine position with head and neck placed neutrally. Anterior cervical soft tissue measurement will be performed in the transverse plane with a 13-6 MHz linear USG probe (Sonosite M-Turbo), including the hyoid bone, thyrohyoid membrane and anterior vocal cord junction. At the level of the hyoid bone, the minimum distance between the hyoid bone and skin (HCM) will be measured and recorded; at the level of the thyrohyoid membrane, the distance between the epiglottis midpoint and skin (ECM) between the hyoid bone and thyroid cartilage; and at the level of the vocal cord, the distance between the vocal cord anterior junction and skin (VCM) will be measured and recorded.

Train of four (TOF) monitoring will be applied to all patients along with standard anesthesia monitoring. Standard induction of anesthesia, 2 mg/kg propofol, 2 mcg/kg fentanyl, 0.6 mg/kg rocuronium as standard to be done intravenously. Mask ventilation will be done with a disposable plastic mask. The Han Scale will be used to assess difficult mask ventilation. (Class 1- Easy mask ventilation, Class 2- Oral airway / adjuvant requirement with/without NMBA,

Class 3- Inadequate, difficult and unstable two practitioners with/without NMBA, Class 4- Impossible with/without NMBA ventilation) The laryngoscopy procedure will be performed by an anesthesiologist who has a minimum of 2 years of anesthesia experience and does not know about USG measurements, with an appropriate size Macintosh blade, after adequate muscle relaxation. The laryngoscopy image will be evaluated with the Cormack-Lehane classification. (Class 1- Glottis fully visible, Class 2- a. Glottis partially visible b. Only arytenoid cartilages visible, Class 3- Only epiglottis visible, Class 4- Epiglottis or glottis not visible) Han Scale 3-4 difficult mask ventilation, Cormack-Lehane 2b-4 will be considered difficult laryngoscopy.

[figure not shown]

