### UPPER LIP BITING TEST

If he can bite his upper lip above the vermilion with his lower incisors

If he can bite his upper lip under the vermilion with his lower incisors

Class 3- If he cannot bite his upper lip with his lower incisors

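### The upper lip bite rule has no not-assessable category, so read literally it grades patients without lower incisors class 3, difficult, because of missing teeth

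*Protocol*

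**What the plan says.** In Methods and Materials, all three bite classes depend on what the patient can do with the lower incisors. For the worst class, "if the patient cannot bite the upper lip with the lower incisors, he/she will be evaluated as class 3". The decision rule follows: "class 1 and 2 will be considered as easy and class 3 as difficult intubation criteria". The section Upper Lip Biting Test repeats the definition: "Class 3- If he cannot bite his upper lip with his lower incisors". Neither place says what to record when there are no lower incisors to bite with.

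Eligibility is broad: "A total of 150 patients ages between 18-80 years". The exclusions are these: "Patients with facial and cervical trauma or cancer surgery, tracheostomy or thyroid surgery, non-cooperative patients and pregnant women will be excluded". None of them removes patients who lack lower incisors.

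Teeth are mentioned once more in the pre-operative evaluation: "mouth opening and distance between incisors will be measured to evaluate the dentition".

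The stated aim in the Introduction is that "it is aimed to determine the correlation between ultrasonographic measurements" and difficult mask ventilation (Han Scale) and difficult laryngoscopy (Cormack-Lehane). The bite test is not part of that aim.

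**The concern.** The easy/difficult split of the bite test is meant to flag a difficult airway. A patient without lower incisors cannot satisfy class 1 or class 2 as worded, however freely the jaw moves. The literal rule therefore gives class 3, which counts as difficult. The grade then reflects tooth loss and not the feature the test is meant to measure.

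The error runs in one direction only, towards difficult. It arises at the bedside, so a later analysis can separate missing teeth from limited jaw movement only if the site recorded which applied. At stake is the measured accuracy of one bedside predictor, should it be analysed against Cormack-Lehane grade.

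**Working it through.** **What the text fixes.** There is no figure in the protocol to reproduce; the point rests on the wording.

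1. Classes 1 and 2 each require a bite with the lower incisors, and class 3 is the inability to make one. Without lower incisors, only class 3 fits.
2. The exclusion list lets such patients enrol.
3. The dentition sentence names two distances. Neither is a code for presence or absence of lower incisors. A blank inter-incisor distance might hint at missing teeth, but a gum-to-gum value might be entered instead, and the protocol does not say which. Nothing ties either entry to the bite class.

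**How large the effect could be (illustration).** Inputs:

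- N = 150, from Methods and Materials.
- p = 0.155, the background rate of difficult intubation quoted in the Introduction for BMI above 35 kg/m². It is used only for scale: the trial enrols from BMI 30, and its own criterion is "Cormack-Lehane 2b-4 will be considered difficult laryngoscopy".
- e, the share without lower incisors: not in the documents. Assumed 1%, 2%, 5% and 10%.
- sp, specificity if tooth loss did not affect the grade: not in the documents. Assumed 0.90 and 0.95.
- Assumed further: tooth loss is unrelated to difficulty and to the grade the patient would otherwise have had, and every such patient is graded class 3.

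Formulas:

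- Non-difficult patients: N(1−p) = 150 × 0.845 = 126.75, about 127.
- Specificity afterwards: sp(1−e).
- Added false positives: N(1−p) × e × sp.
- Sensitivity afterwards: s + (1−s)e.
- Youden index afterwards: s + (1−s)e + sp(1−e) − 1 = (1−e)(s + sp − 1).

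| e | Patients without lower incisors (150e) | Added false positives, sp 0.90 | Added false positives, sp 0.95 | Specificity from 0.90 | Specificity from 0.95 |
|---|---|---|---|---|---|
| 1% | 1.5 | 1.1 | 1.2 | 0.8910 | 0.9405 |
| 2% | 3.0 | 2.3 | 2.4 | 0.8820 | 0.9310 |
| 5% | 7.5 | 5.7 | 6.0 | 0.8550 | 0.9025 |
| 10% | 15.0 | 11.4 | 12.0 | 0.8100 | 0.8550 |

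Example, last row: 126.75 × 0.10 × 0.95 = 12.0, and 0.95 × 0.90 = 0.855.

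The loss of specificity is e × sp, from 0.01 × 0.90 = 0.009 to 0.10 × 0.95 = 0.095, or about 1 to 10 percentage points. The gain in sensitivity is (1−s)e, which cannot exceed e. The net effect on the Youden index is a relative loss of e, here 1% to 10%. The false-positive counts scale with (1−p), so even with p near zero the largest would be 150 × 0.10 × 0.95 = 14.25.

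**The case against.** **The test might simply not be done.** The procedure asks the patient to bite with the lower incisors, so it presupposes them, and an assessor could leave the test blank when they are absent. That is possible, but the protocol does not say so, and the class 3 wording covers inability without regard to cause. What stands is that misgrading depends on assessors applying the rule literally. The protocol also says its cut-off follows the study that introduced the test; whether that study dealt with missing teeth cannot be checked from the documents.

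**Three stronger readings are tempting and are not supported.**

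- A reader might infer that dentition is never recorded. The protocol plans to evaluate it. The weakness is that the distances named do not state whether lower incisors are present.
- A reader might infer that ultrasound will look better by comparison. The protocol states no comparison of ultrasound with the bite test. The ultrasound distances, Han Scale and Cormack-Lehane grade do not depend on the bite class.
- A reader might infer that a large part of all class 3 grades would be artefacts. With an assumed class 3 rate of 10% in patients with teeth, counting every patient without lower incisors gives 0.05/(0.05 + 0.095) = 34% at e = 5% and 0.10/(0.10 + 0.09) = 53% at e = 10%. This overcounts: on the same assumption one in ten of these patients would have been class 3 anyway, so the shares become 0.9 times as large, about 31% and 47%. Both inputs are assumptions, so no such share can be attributed to this trial.

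**Lost specificity is only one side.** Sensitivity rises at the same time, so the net loss of discrimination is modest. This is correct and limits the weight of the point.

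**Conclusion.** The point holds as a minor defect in a stated measurement rule. As written, the bite test grades patients without lower incisors difficult for a reason unrelated to jaw movement, and the planned dentition measurements do not reliably identify them afterwards. The bias is confined to this one bedside test, which lies outside the stated aim.

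Its size cannot be fixed from the documents. About 1 to 12 extra false positives in 150 patients follows from assumed shares of 1% to 10%, assumed specificities of 0.90 to 0.95, a borrowed 15.5% rate of difficulty, literal use of the rule, and independence of tooth loss and difficulty. If laryngoscopy is easier in these patients there would be more false positives, and if it is harder, fewer.

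**What to change.** In Methods and Materials and in the section Upper Lip Biting Test, add that the test is coded not assessable, and not class 3, when the lower incisors are absent. On the case record form, record explicitly whether lower incisors are present, and mark each mouth-opening value as inter-incisor or inter-gum. Leave not-assessable patients out of any analysis of the bite test and keep them in all ultrasound analyses.

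The cost is a sentence in each section, a tick-box for lower incisors and a marker for mouth opening. The bite test's estimates would rest on slightly fewer patients: on the assumed range, about 2 to 15 of 150. The change is easy before enrolment. Afterwards it may not be possible to recover who lacked lower incisors.
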